4. STUDY POPULATION

4.1 Population (base)

Study population:

Patients with c-MET positive, advanced SGC

- c-MET positivity
 - Immunohistochemistry
 - c-MET expression will be evaluated by immunohistochemical staining on a biopsy of the primary tumor (in case of locally advanced or locally recurrent disease) or a biopsy of metastasis (in case of metastatic disease). The D1C2 antibody (Cell Signaling®) will be used.
 - The staining pattern will be scored as cytoplasmic and membranous staining using a semiquantitative scoring system (negative / weak / moderate / strong). Weak, moderate and strong cytoplasmic and/or membranous staining will be regarded as c-MET positive disease.
 - NGS
 - C-MET mutations and amplifications will be assessed using Next-Generation Sequencing (NGS) of Formalin-Fixed, Paraffin-Embedded (FFPE) tissue using Single Molecule Molecular Inversion Probes (smMIP's).¹⁴
 - MET (NCBI Reference Sequence NM_001127500.2) will be sequenced in the following regions: codon 168, 375, 982-1027, 1230-1284, 1304.
- Advanced SGC
 - Advanced SGC is defined as either/or
 - Locally advanced SGC
 - Locally recurrent SGC
 - Metastatic SGC
- Patients will be analyzed in 3 cohorts (see statistical plan for more information)
 - SDC: n=9/17 patients
 - ACC: n=9/17 patients
 - In this cohort, patients with advanced ACC originating from the salivary glands and ACC originating from other body parts will be included.
 - Other SGC's: n=9 patients

Source population:

Study participants will be drawn from the following source population:

- Patients with SGC who are treated at the Department of Medical Oncology of the Radboudumc.
- Patients with SGC who are referred to the Department of Medical Oncology of the Radboudumc in order to evaluate eligibility to participate in this study.
- Patients with SGC who heard or read about this study and contact the investigators to ask whether they can take part in the study. Potential participants will not be actively recruited. However, there will be a message on the website of Dutch Salivary Gland Cancer Patient Platform: <http://speekselklierkanker.org/>. This message is added to this submission (see 'E3 Wervingsmateriaal').

4.2 Inclusion criteria

In order to be eligible to participate in this study, a patient must meet all of the following criteria:

- Disease specific
 - locally advanced, recurrent, and/or metastatic SGC (excluding sarcomas and mesenchymal tumors)
 - c-MET positive disease (see paragraph 4.1)
 - Measurable disease per RECIST version 1.1
 - Cohort-specific criteria
 - SDC cohort:
 - Direct inclusion (no objective tumor growth prior to inclusion needed)
 - ACC cohort:
 - Inclusion after objective growth in the last three months or complaints due to the disease
 - Other SGC's
 - Inclusion after objective growth in the last three months or complaints due to the disease
- General conditions
 - Age \geq 18 years
 - Eastern Cooperative Oncology Group performance status of 0 or 1.
 - Normal number of neutrophils and thrombocytes
 - Liver function:
 - ALT and AST $<$ 2.5 x upper limit of normal (ULN)
 - Total bilirubin \leq 1.5 x ULN (except for Gilbert's syndrome)
 - Serum albumin \geq 28 g/L
 - Renal function:
 - Creatinine $<$ 1.5 x ULN or calculated creatinine clearance \geq 40 ml/min
 - Urine protein/creatinine ratio \leq 113.1 mg/mmol (\leq 1 mg/mg) or 24-hour urine protein $<$ 1 g
 - Hemoglobin A1c (HbA1c) \leq 8% or a fasting serum glucose \leq 9 mmol/l

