1. INTRODUCTION AND RATIONALE

SGC is a rare cancer. The annual incidence rate ranges from 0.4-2.6 cases per 100,000 people. Besides, SGC's are histological diverse. Twenty-four histological types can be distinguished.¹ Primary treatment consists of resection of the affected salivary gland and a neck dissection, mostly followed by postoperative radiotherapy. Treatment options for patients with locally recurrent and/or metastatic disease (later: advanced disease) systemic treatment options are limited to androgen deprivation therapy (ADT) and HER2-targeted therapies in selected cases. Chemotherapy may be used for palliation, but the effect is limited. Therefore, new treatment options for advanced SGC are urgently warranted.

Cabozantinib is an oral, small-molecule inhibitor of tyrosine kinases, including c-MET, VEGFR, and AXL. In preclinical models, cabozantinib has been shown to suppress tumor growth, angiogenesis, and metastasis.² In clinical practice, it has been approved for treatment of advanced renal cell carcinoma in patients who received prior anti-angiogenic therapy (cabometyx® tablets),³ and treatment of progressive, metastatic medullary thyroid cancer (Cometriq® capsules).⁴ Next to this, it has shown promising results in bone metastases of castration-resistant prostate cancer.⁵

Cabozantinib may also be of value in the treatment of advanced SGC because c-MET, one of the targets of cabozantinib, is frequently overexpressed in SGC. In ACC, c-MET overexpression has been shown in 53.2% of patients.⁶ In SDC, c-MET overexpression has been shown in 39.7% of patients.⁷

No data are available on the efficacy of cabozantinib in SGC. We will conduct a phase II, single arm clinical trial to investigate the efficacy of cabozantinib in c-MET positive SGC. Three patient groups will be included: (1) advanced SDC, (2) advanced ACC, and (3) advanced SGC of other subtypes. As ACC can originate in the salivary glands, but also in other parts of the body, such as lung, trachea, breast and cervix, these patients can also be included in the study and will be analyzed in the cohort with advanced ACC patients.

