2. OBJECTIVES

Objectives will be analyzed separately in all 3 cohorts of c-MET positive, advanced SGC: (1) SDC, (2) ACC originated in the salivary glands or other sites of the body, (3) other SGC's

Primary Objective

- Assess the ORR. ORR is defined as the sum of the complete remissions plus partial responses.⁹ The best response will be used in each patient.

Secondary Objectives

- Assess the PFS. PFS will be defined as time from study enrollment until disease progression or death.
- Assess the OS. OS will be defined as time from study enrollment until date of death of any cause.
- Assess the DoR. DoR is defined as time from study enrollment until date of documented tumor progression or death
- Assess the toxicity of cabozantinib. Toxicity will be scored according to NCI CTC common criteria v 4.0.¹⁰
- Assess the QoL of patients treated with cabozantinib using EORTC questionnaires.
- Assess the response rate by using continuous tumor shrinkage end-points, as was advocated by Billingham et al¹¹ and Wason et al.¹²
- ctDNA will be assessed to evaluate whether response and disease progression can be predicted.

More details about the definitions and analysis of primary and secondary outcomes are described in chapter 8.1.

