10.2 Secondary study parameter(s)

- Assess the PFS
 - PFS will be estimated by a Kaplan-Meier curve
 - In SDC patients, PFS will be compared to PFS in AR-positive SDC patients which received ADT^{17,18} and HER2-positive SDC patients which received docetaxel plus trastuzumab.¹⁹
 - In ACC patients, PFS will be compared to PFS in ACC patients which received mitoxantrone monotherapy,^{20,21} vinorelbine monotherapy,²² epirubicin monotherapy,²³ or cisplatin plus anthracycline combination therapies²⁴
 - In other SGC patients, PFS will be described per individual case.
- Assess the OS
 - OS will be estimated by a Kaplan-Meier curve
 - In SDC patients, OS will be compared to a historical cohort of patients receiving best supportive care and a cohort receiving ADT.¹⁸
 - In ACC patients, median OS after disease recurrence is 6.4 years, and median OS after metastasis is 3.7 years.²⁵ OS of our study patients will be compared to these data and to OS data of phase II studies in ACC mentioned above (assess the PFS).
 - In other SGC patients, survival will be described per individual case
- Toxicity and QoL questionnaires will be described using simple descriptive statistics.
- Assess the response rate of patients with advanced SGC treated with cabozantinib by using continuous tumor shrinkage end-points, as was advocated by Billingham et al¹¹ and Wason et al.¹²
- Tumor shrinkage will be shown in a waterfall plot.

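### Section 4.2 admits only salivary gland cancer, while the ACC cohort is defined to include ACC of other organs; the wording needs reconciling, and the secondary ACC historical contrasts should be restricted to like sites

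*Combined protocol and SAP*

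**What the plan says.** Section 4.2 is conjunctive: "a patient must meet all of the following criteria". The first criterion is "locally advanced, recurrent, and/or metastatic SGC (excluding sarcomas and mesenchymal tumors"). The only line specific to the ACC cohort is "Inclusion after objective growth in the last three months or complaints due to the disease", which says nothing about site of origin.

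The population statement in section 4.1 reads "Patients with c-MET positive, advanced SGC", and each of the three source-population bullets in that section is limited to patients with SGC.

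Three other places define the ACC cohort more widely:

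- Section 1 observes that ACC also arises outside the salivary glands, "such as lung, trachea, breast and cervix, these patients can also be included in the study and will be analyzed in the cohort with advanced" (the sentence ends by naming the second cohort).
- Section 2 describes the second cohort as "ACC originated in the salivary glands or other sites of the body".
- Section 4.1, directly under the 9/17 target for ACC, says that "patients with advanced ACC originating from the salivary glands and ACC originating from other body parts will be included".

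Section 10.2 compares ACC progression-free survival (PFS) with the treatment series in references 20 to 24. For overall survival (OS) it cites medians of 6.4 years after recurrence and 3.7 years after metastasis from reference 25, and says "OS of our study patients will be compared to these data" and to the phase II series already named. No split by site of origin is planned.

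**The concern.** Section 4.2 is the text that staff apply. Under section 11.2 the baseline visit opens with a check of the inclusion and exclusion criteria. Eligibility is then recorded on the case report form (12.1) and verified against source documents (12.2). A patient with ACC of the lung, breast or cervix does not have SGC in the ordinary sense, and section 1 itself contrasts those organs with the salivary glands. Someone applying 4.2 word for word could therefore turn away a patient whom the sponsor means to enrol, or a monitor could query one already enrolled.

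A second, separate matter arises once such patients are in the cohort. The historical ACC figures in 10.2 appear to come only from head-and-neck or salivary disease. The pooled cohort's PFS and OS would then be read against a population with a different mix of primary sites, and the plan neither separates the sites nor comments on the difference.

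**Working it through.** **Step 1. Eligibility wording side by side.**

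| Place | Who it covers |
|---|---|
| 4.2, first criterion | SGC only |
| 4.2, ACC cohort line | growth or complaints; silent on site |
| 4.1, population statement | SGC only |
| 4.1, three source bullets | SGC only |
| 4.1, ACC cohort text | salivary ACC and ACC of other body parts |
| 2, cohort list | salivary ACC and ACC of other sites |
| 1, last part | names lung, trachea, breast and cervix; analysed with ACC |

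Because 4.2 requires every criterion to be met and the ACC line does not widen the first one, the literal rule is narrower than the cohort definition. No exclusion criterion in 4.3 removes non-salivary ACC, and three places state the intent to include it. The rule and the definition disagree, but the direction of the correction is not in doubt.

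**Step 2. Do these patients count toward 9/17?** Yes. Section 1 assigns them to the ACC cohort for analysis, and 4.1 puts their inclusion under the ACC target of 9/17.

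**Step 3. Comparator populations, judged by the titles in the reference list.**

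| Reference | Used for | Population in title |
|---|---|---|
| 20 (mitoxantrone) | PFS, OS | ACC of the head and neck |
| 21 (mitoxantrone) | PFS, OS | ACC of the head and neck |
| 22 (vinorelbine) | PFS, OS | recurrent salivary gland malignancies |
| 23 (epirubicin) | PFS, OS | ACC of the head and neck |
| 24 (systematic review, for cisplatin plus anthracycline) | PFS; OS where phase II data | ACC of the salivary glands |
| 25 (outcome series) | OS medians | ACC of the head and neck |

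All six are head-and-neck or salivary; none names ACC of another organ. Only the titles could be examined.

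**Step 4. Is the primary test touched?** Inputs from 4.4 and 10.1: stage 1 has 9 patients and stops on 0 responses; the final 17 lead to rejection on more than 2; the response rates are 5% and 25%. The probability of rejection at true rate p is

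P(reject) = P(X1 = 1)·P(X2 ≥ 2) + P(X1 = 2)·P(X2 ≥ 1) + P(X1 ≥ 3), with X1 ~ Bin(9, p) and X2 ~ Bin(8, p).

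- p = 0.05: 0.2985 × 0.0572 + 0.0629 × 0.3366 + 0.0084 = 0.0466 (plan: 0.047).
- p = 0.25: 0.2253 × 0.6329 + 0.3003 × 0.8999 + 0.3993 = 0.812 (plan: 0.81).

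The plan's figures reproduce. The formula uses only the fixed rates 5% and 25% and the cohort counts. Nothing from references 20 to 25 enters it, and neither proposed change alters it.

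**The case against.** The best defence is that the protocol uses SGC as an umbrella term. Section 2 introduces all three cohorts as SGC and then defines the second as ACC of salivary or other origin; section 4.1 does the same under its SGC heading. Read that way, the ACC line in 4.2 inherits the cohort definition given one section earlier, and no one following the protocol as a whole would record a violation. This stands in large part: the intent is plain, and the defect is one of wording. It does not remove the point, because section 1 sets the salivary glands apart from the other organs, and 4.2 neither defines SGC broadly nor refers back to the cohort text.

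On the comparators, the defence is that the contrasts are secondary and carry no test, margin or decision rule, that the source populations are known only from titles, and that nothing in the documents shows that ACC outcomes vary by primary site. All of that stands and limits the second part to a matter of clean reporting.

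Two stronger readings are tempting. A reader might infer that non-salivary cases are at once ineligible and wrongly compared. The documents do not support the pair: a patient excluded under 4.2 is never compared, and the stated intent is to include. A reader might also infer that, with thresholds of 1 in 9 and 3 in 17, a disputed non-salivary responder could overturn the cohort's result. Sections 1 and 4.1 already say that these patients count, and a single patient can tip any design of this kind.

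**Conclusion.** The point holds as a minor one, in two parts.

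First, 4.2 and the SGC-only lines in 4.1 contradict the ACC cohort as defined in sections 1, 2 and 4.1. The consequence is confined to how eligibility is checked and documented.

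Second, the ACC historical contrasts in 10.2 would set a cohort of mixed primary sites against series that are, by title, confined to head-and-neck or salivary disease. These contrasts are descriptive and secondary.

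The primary response-rate test, its type I error of 0.047, its power of 0.81 and its 0/9 and 2/17 rules are unaffected.

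No numerical size can be put on the second part. The feasibility text in 4.4 does not separate non-salivary ACC, and the documents give no outcome by site. For the same reason, a reader should not conclude that the historical figures fail to describe these patients or that pooling sites weakens the primary test: any figure would rest on an assumed share and an assumed response rate. The verdict assumes that the reference titles describe their populations correctly.

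**What to change.** In section 4.2, extend the first criterion so that, for the ACC cohort, ACC of any primary site qualifies. In section 4.1, bring the population statement and the three source bullets into line with the cohort text.

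In section 10.2, limit the ACC comparisons with references 20 to 25 to patients with salivary or head-and-neck primaries, and list PFS and OS of patients with other primaries separately. Say beforehand how a site such as the trachea is classed, since section 1 names it among the non-salivary sites. Leave the response-rate analysis of the whole ACC cohort as it is.

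The cost is a few lines of text. Primary tumour location is already among the variables in 8.2.1, so no new data are needed. As an inclusion criterion is touched, the sponsor would have to classify the change under 12.3. The one statistical downside is a slightly smaller group in the historical contrast.

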4.3 Exclusion criteria

- General conditions
 - A known allergy for cabozantinib or its components
 - Long QT-syndrome
 - Pregnancy or lactation
 - Patients (M/F) with reproductive potential not implementing adequate contraceptives measures
 - Known brain metastases or cranial epidural disease unless adequately treated with radiotherapy and/or surgery and stable for at least 3 months before inclusion
 - Major surgery within 3 months before randomization. Complete wound healing from major surgery must have occurred 1 month before inclusion and from minor surgery at least 10 days before inclusion
 - Uncontrolled illness including, but not limited to
 - Cardiovascular disorders including symptomatic congestive heart failure, unstable angina pectoris, or serious cardiac arrhythmias
 - Uncontrolled hypertension defined as sustained systolic BP > 150 mm Hg, or diastolic BP > 100 mm Hg
 - Stroke (including TIA), myocardial infarction, or other ischemic event within 6 months before inclusion
 - Serious active infections
- Concomitant treatments
 - Concomitant (or within 4 weeks before inclusion) administration of any other experimental drug under investigation.
 - Concurrent treatment with any other anti-cancer therapy.
 - Concomitant anticoagulation.
 - Low dose aspirin for cardioprotection and low dose LMWH are permitted.
 - Radiation therapy within the last 4 weeks before inclusion

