4.4 Sample size calculation

The Simon two-stage design¹⁵ will be used, with a null hypothesis of at most 5% response rate (not warranting further investigation) and an alternative hypothesis of at least 25% response rate (leading to further investigation). The statistical error rates of the design are $\alpha = 0.05$ and $\beta = 0.80$. The first stage consists of 9 patients per cohort ((1) SDC, (2) ACC) evaluable for response. If 0 responses out of the first 9 evaluable patients are observed, the study will be stopped with the conclusion that the drug should not be further investigated. In any other situation, the study will be continued until 17 patients are evaluable for response per cohort. If ≤ 2 responses out of these 17 patients are observed the study will accept the null hypothesis, with the conclusion that the drug should not be investigated further. If > 2 responses out of 17 patients are observed, the null hypothesis will be rejected with the conclusion that the drug should be further investigated. In the third cohort (other SGC) 9 patients will be included to evaluate the efficacy of cabozantinib in other subtypes of c-MET positive SGC. Because different subtypes are included in this cohort, these results are hypothesis forming but will not be used for statistical analysis. Therefore, this study cohort will be closed after the first stage with 9 patients.

Feasibility analysis:

The Radboud university medical center is a tertiary referral center for head and neck cancer and SGC in particular, receiving referrals from all other academic medical centers and the Dutch Cancer Institute in the Netherlands. In 2016 and 2017 approximately 80-90 new locally recurrent or metastatic SGC patients (40% SDC, 40% ACC, 20% other SGC's) visited our outpatient department. Next to this, we closely collaborate with the SGC patient network in the Netherlands. Therefore we believe it is feasible to enroll 17 SDC patients, 17 ACC patients and 9 other SGC patients in two years.

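### Section 4.3 sets no look-back for standard systemic anti-cancer therapy, so residual shrinkage from a recently stopped drug could be counted as a cabozantinib response

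*Combined protocol and SAP*

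**What the plan says.** Section 4.3 treats three kinds of prior or concomitant anti-cancer treatment differently:

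- Experimental drugs: "Concomitant (or within 4 weeks before inclusion) administration of any other experimental drug under investigation" is an exclusion.
- Radiotherapy: "Radiation therapy within the last 4 weeks before inclusion" is an exclusion.
- Everything else: only "Concurrent treatment with any other anti-cancer therapy" is an exclusion. No interval is attached.

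Section 4.2 sets cohort-specific entry rules. For SDC it is "Direct inclusion (no objective tumor growth prior to inclusion needed". For adenoid cystic carcinoma (ACC) and other salivary gland cancers (SGC), either growth in the previous three months or disease complaints suffices. Section 13.1g says that objective growth is required for the types other than SDC and does not mention the complaints route.

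Prior systemic therapy is foreseeable. Section 1 says that "systemic treatment options are limited to androgen deprivation therapy (ADT) and HER2-targeted therapies in selected cases" and adds palliative chemotherapy. Section 10.2 uses androgen deprivation and docetaxel plus trastuzumab as the SDC comparators for PFS.

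The primary endpoint (8.1.1) is best RECIST 1.1 response, verified by an independent committee. The baseline CT is at week 0 (8.4). Section 5.2 bars co-intervention during the study. Section 8.2.1 records earlier palliative treatments as history, and no eligibility or analysis rule uses them.

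**The concern.** In a single-arm trial the count of responders is all the evidence on the primary question. Best response is measured from the week 0 scan and has no rule on attribution. The committee can confirm that a tumour shrank by the required amount, but it is not asked why.

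Take a patient who stops an effective drug for toxicity, or at the planned end of a course, and enters soon afterwards. The week 0 scan may then be taken while the earlier drug is still acting. Further shrinkage large enough for PR would be credited to cabozantinib. In the SDC cohort no growth requirement stands in the way. In ACC and other SGC the growth requirement helps, but entry on complaints bypasses it.

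The numbers are small: 1 response in 9 opens stage 2, and 3 in 17 lead to the conclusion that the drug merits further study. A single misattributed response therefore carries weight.

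**Working it through.** **Inputs from the plan.** Null rate 0.05, target rate 0.25, stop at 0 of 9, reject the null at 3 or more of 17 (4.4, 10.1). The rule applies to the SDC and ACC cohorts; 4.4 keeps the third cohort out of the formal test. Stated operating characteristics: type I error 0.047, power 0.81 (10.1). Section 4.4 prints 0.80 as beta; the value works only as power.

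**Input not in the plan.** The frequency of carry-over responses. Everything below that uses it is an assumed scenario.

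**Step 1: reproduce the plan.** With true rate p,

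P(reject) = Σ over x = 1..9 of P(Bin(9,p) = x) × P(Bin(8,p) ≥ 3 − x).

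At p = 0.05:

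- x = 1: 0.2985 × 0.0572 = 0.0171
- x = 2: 0.0629 × 0.3366 = 0.0212
- x ≥ 3: 0.0084
- Sum: 0.0466, which is the stated 0.047.

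At p = 0.25 the same sum gives 0.812, matching the stated 0.81. The chance of stopping at stage 1 when p = 0.05 is 0.95⁹ = 0.63.

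**Step 2: exactly one carry-over responder, the other 16 patients at 5%.**

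- Among the first 9: stage 1 is passed automatically, and 2 or more responses are needed from the other 16. P = 1 − 0.95¹⁶ − 16 × 0.05 × 0.95¹⁵ = 1 − 0.4401 − 0.3706 = 0.189.
- Among the last 8: stage 1 must still produce a response. With one in stage 1, one more is needed from the 7 others in stage 2: 0.2985 × (1 − 0.95⁷) = 0.2985 × 0.3017 = 0.0901. With two or more in stage 1: 0.0712. Sum 0.161.
- In random order: (9/17) × 0.189 + (8/17) × 0.161 = 0.176.

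**Step 3: each patient has an assumed probability c of a carry-over response.** The effective null rate is 0.05 + 0.95c, put into the formula of step 1.

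| Assumed c | Effective rate | P(reject), inactive drug |
|---|---|---|
| 0 | 0.0500 | 0.047 |
| 0.5% | 0.0548 | 0.058 |
| 1% | 0.0595 | 0.071 |
| 2% | 0.0690 | 0.10 |
| 5% | 0.0975 | 0.21 |
| 10% | 0.1450 | 0.43 |

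**Step 4: is the gap closed elsewhere?** Section 5.2 covers treatment during the study, not before it. Section 8.2.1 records prior treatment but does not act on it. Section 13.1g explains why SDC patients need not show growth, but that is a rationale, not an entry check. The normal neutrophil and thrombocyte criterion in 4.2 would delay entry after some chemotherapy, but it is not directed at androgen deprivation or trastuzumab. None of these sets an interval or uses progression since the last therapy.

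**The case against.** **Shrinkage alone does not count.** A reader might infer that any tumour still shrinking at entry becomes a cabozantinib response. The documents do not support that. The shrinkage must reach PR or CR against the week 0 scan, after the earlier drug has been stopped, and be verified independently. Part of the regression is already in the baseline. This stands, so the point is conditional.

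**The size is assumed.** The one-patient result presupposes the event, and the values of c are not in the documents. Only patients who recently stopped a drug, were still regressing and went on to PR can contribute. If, for illustration, 20% of a cohort had recently stopped a drug, c = 10% would need half of them to reach PR afterwards. At c = 0.5% the error rate moves only to 0.058. This stands too: the calculation shows how sensitive the rule is, not how large the bias will be.

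**The intended population is different.** Section 13.1g calls the condition unstable at inclusion and SDC aggressive, and 13.2 stresses the lack of alternatives. Most patients would probably enter because their disease is progressing. That is a fair reading of intent, but the criteria do not require it.

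**PFS.** A reader might infer that carry-over also lengthens PFS. The direction is not established: a baseline taken during regression is smaller, so regrowth from it may be scored as progression sooner.

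**Mandatory progression for pretreated SDC.** A reader might conclude that these patients must show progression before entry. That is a debatable clinical eligibility choice in a disease the protocol calls aggressive, and the statistical argument does not require it.

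**Conclusion.** The gap is real. The plan applies a look-back to two kinds of prior anti-cancer treatment and none to the kind that SDC patients are most likely to have had according to its own introduction. Followed as written, the plan could credit residual shrinkage to cabozantinib. The exposure is widest in SDC and smaller in ACC, where the complaints route leaves it partly open.

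For an inactive drug the false-positive chance rises from 0.047 to about 0.18 with one carry-over responder, and to between 0.058 and 0.43 across the assumed range of c. These figures rest on the stated 9/17 rule, a true rate of 5%, independence between patients, and a carry-over frequency that the documents do not give. A reader might take 0.18 or more as the trial's actual error rate; nothing in the documents supports that. The point is a worthwhile, low-cost correction (should fix), not a demonstrated flaw in the result.

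**What to change.** 1. **Section 4.3.** Reconcile the three bullets so that other anti-cancer therapy is excluded both concurrently and within a stated interval before inclusion, with the week 0 CT made after that interval. The sponsor sets the length; 4 weeks is the interval 4.3 already uses for experimental drugs and radiotherapy.
2. **Sections 4.2 and 13.1g.** Reconcile the growth requirement described in 13.1g with the complaints route that 4.2 allows for ACC and other SGC.
3. **Section 10.1.** Using the history already collected under 8.2.1, list for each responder the last systemic therapy, its stop date and whether progression was documented since. Add a sensitivity analysis of the response count that treats as non-responders those who stopped therapy within the look-back without documented progression. This also covers anyone enrolled before the change.

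**Cost.** A short amendment. The sample size of 9/17 and the stated error rates stay as they are, and no study procedure is added. A few pretreated patients may wait before entry, which the sponsor must weigh in setting the interval. The sensitivity count may be slightly less favourable than the primary one.
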